1.0 Objectives

1.1 Study Objectives

The objective of this study is to determine whether treatment with random nicotine delivery via nicotine film both before and after the quit date will facilitate cessation relative to treatment with steady state delivery or placebo. We hypothesize that smoking cessation will be greater in subjects assigned to a random nicotine delivery regimen (as compared to those assigned to a steady state or placebo regimen). The nicotine film product is not part of the standard of care and is not available in non-investigational settings in the United States.

1.2 Primary Study Endpoints

The primary endpoints for the study include the percent reduction in the number of cigarettes smoked and the accompanying percent reduction in exhaled carbon monoxide (CO) levels.

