1.3 Secondary Study Endpoints

The secondary endpoints include subjective ratings of the films and side effects.

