7.4.6.5 Prior and Concomitant Therapy

Concomitant medication use will be collected at baseline and regularly throughout the study to serve as covariates during analysis and to monitor participant health conditions. Participants currently using FDA approved cessation medications will be excluded. Should a participant start a medication during the randomized, double-blind phase of the study that would interfere with their ability to participate, they may be withdrawn from the study.

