8.2 Sample size determination

Previous studies have shown the effects of NRT on cessation in sample sizes that are comparable to (e.g., [name], et al., 1992; Rose, et al., 1998; Rose, et al., 2006) the one proposed here (n=15 per treatment arm). Based upon such work, we are confident that we will have sufficient power to achieve the aim of the proposed research.

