8.3 Statistical methods

Paired sample t-tests (or nonparametric Wilcoxon Rank-Sum tests) will be used to examine changes in the outcome measures (CPD, CO, subjective measures, BP, HR) from baseline.

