10.7 Statistical tests

Statistical methods will be used to analyze the safety data to determine whether harms are occurring. Paired sample t-test (or nonparametric Wilcoxon Rank-Sum test) will be used to examine the changes in the outcome measures (CPD, CO, subjective measures, BP, HR) from the baseline.

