12.2 Potential Benefits to Others

Society as a whole will benefit from the research because it is expected to provide important information on the efficacy of nicotine film and random nicotine delivery as a potential method for smoking cessation.

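### The objective is a between-arm comparison of quitting, but the plan defines no abstinence outcome and specifies no comparison of arms

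*Combined protocol and SAP*

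**What the plan says.** **The question.** Section 1.1 is comparative and about quitting: "We hypothesize that smoking cessation will be greater in subjects assigned to a random nicotine delivery regimen", with the steady-state and placebo regimens as comparators. Section 12.2 says of the research that "it is expected to provide important information on the efficacy of nicotine film and random nicotine delivery as a potential method for smoking cessation". Section 8.2 supports 15 per arm by precedent: "Previous studies have shown the effects of NRT on cessation in sample sizes that are comparable". At Visit 3 (section 7.2.4) every participant is told to stop smoking from the next morning.

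**The outcomes.** Section 1.2: "The primary endpoints for the study include the percent reduction in the number of cigarettes smoked", plus the percent reduction in exhaled CO. It names neither a visit nor a baseline. Section 1.3: "The secondary endpoints include subjective ratings of the films and side effects".

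**The analysis.** Section 8.3 is one sentence: "Paired sample t-tests (or nonparametric Wilcoxon Rank-Sum tests) will be used to examine changes in the outcome measures", listed as CPD, CO, subjective measures, BP and HR, from baseline. Section 10.7 repeats it for safety; the same tests "will be used to examine the changes in the outcome measures (CPD, CO, subjective measures, BP, HR) from the baseline". Section 7.4.6.5 adds "Concomitant medication use will be collected at baseline and regularly throughout the study to serve as covariates during analysis", but no model that takes covariates is given.

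**The concern.** Two things needed to answer the question in section 1.1 are absent.

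1. **An abstinence outcome.** There is no definition of a quitter, no window, no CO cut-off for abstinence (the 6 ppm in section 3.1 is an entry criterion) and no rule for missing participants. Sections 1.2 and 1.3 both use the word include, which might leave room for more, but the outcomes listed for analysis in sections 8.3 and 10.7 do not contain abstinence either.
2. **A comparison of arms.** Every stated test concerns change from baseline. All three arms are told to quit, so all may fall whatever the regimen, and a within-arm fall says nothing about random delivery.

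If abstinence is derived later from the diary and CO data, its window, cut-off and missing-data rule would be chosen after the data have been seen.

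A smaller gap concerns coding. After Visit 3, cigarettes are entered in the diary only for slips (sections 7.2.4 and 7.2.6). Section 7.4.4 has staff review the logs at each contact, so the information can be obtained, but the plan does not say how a day with no cigarette entry is counted.

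**Working it through.** **Inputs from the protocol.** 45 randomized (section 8.1), three arms, 15 per arm (section 8.2); 3 × 15 = 45 agrees. Section 8.2 gives no alpha, effect size, SD, event rate or power figure, so there is no calculation to reproduce. All other values below are assumptions for illustration, not trial estimates.

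**Step 1: mean reduction does not identify quitting.** Take a mean cigarette reduction of 64% in 15 people, q of whom quit (100% reduction). The non-quitters then average (64 × 15 − 100q)/(15 − q).

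| Quitters of 15 | Non-quitter mean reduction |
|---|---|
| 0 | 64% |
| 3 | 55% |
| 6 | 40% |
| 9 | 10% |
| 10 | −8% (an increase) |

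The same mean therefore fits 0 to 9 quitters (0% to 60%) if non-quitters do not on average increase. CO behaves the same way: 6 quitters with falls of 85% and 9 others averaging 50% give (6 × 85 + 9 × 50)/15 = 64%, which is also the mean if 15 non-quitters average 64%.

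**Step 2: paired tests do not compare arms.** For n = 15, t = mean/(SD/√15) on 14 degrees of freedom.

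| Mean reduction | SD | t | p |
|---|---|---|---|
| 40 | 40 | 3.87 | 0.0017 |
| 40 | 30 | 5.16 | 0.0001 |
| 64 | 40 | 6.20 | < 0.0001 |
| 64 | 30 | 8.26 | < 0.0001 |

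Three arms that all average 40% (SD 40) would each show p = 0.002 with no treatment difference. With 64% in one arm and 40% in another, both paired tests are again significant. The 95% CI half-width for the difference is t(0.975, 28) × SD × √(2/15), with t = 2.048:

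- SD 40: half-width 29.9, so 24 points has CI −5.9 to 53.9.
- SD 30: half-width 22.4, so 24 points has CI 1.6 to 46.4.

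**Step 3: setting within-arm p-values side by side can mislead.** Suppose all arms share the same true standardized change d, so there is no treatment effect. Let π be the power of one paired t-test (noncentral t, n = 15, two-sided 0.05). Random delivery is significant while at least one comparator is not with probability π(1 − π²); all three are significant with probability π³.

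| d | π | Random significant, at least one comparator not | All three significant |
|---|---|---|---|
| 0.5 | 44% | 35% | 8% |
| 0.75 | 77% | 31% | 46% |
| 1.0 | 95% | 9% | 85% |

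**Step 4: an unstated missing-data rule matters.** Assume 5 abstinent in each of two arms, and 4 withdrawn from one arm with unknown status.

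- Missing counted as smoking: 5/15 − 5/15 = 0 points, exact unconditional 95% CI about −34 to 34.
- Observed cases: 5/11 − 5/15 = 45% − 33% = 12 points, CI about −26 to 49.

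The limits of these two intervals depend on the search grid to within about one point.

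**Step 5: precision of a binary outcome.** 1 of 15 abstinent (6.7%) has a Clopper–Pearson 95% CI of 0.2% to 31.9%.

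**The case against.** **The rank-sum test compares independent samples, so an arm comparison may be intended.** The name does fit that, and the design is described as randomized, placebo-controlled and parallel-group. But both sections offer it as the nonparametric alternative to the paired t-test for the same change from baseline, and neither names arms. A slip for the signed-rank test is the likelier reading. At best the text is ambiguous, which still leaves no specified contrast.

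**Percent reduction with CO is a legitimate endpoint for 45 people, and abstinence at 15 per arm is nearly uninformative.** The second part stands. With an assumed doubling of the odds and control rates of 7% to 30%, Fisher's exact test has power of only 1.3% to 6.6%, so abstinence supports estimation, not a powered test. The first part also stands as a design choice, but then section 1.1 should speak of reduction. A quitter does contribute a 100% reduction, yet step 1 shows that the mean does not recover the number of quitters.

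**Baseline is not wholly undefined.** This is partly right. The Time & Events Table labels Visit 1 as Baseline, and section 3.1 refers to CO at the baseline visit. CO is also measured at Visit 2, however, and the pre-treatment cigarette diary runs between the two visits, so section 1.2 should say which values are used.

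**The numbers are hypothetical.** They are. They show what the stated analysis can and cannot distinguish; they do not predict this trial's results.

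**Conclusion.** The concern holds and must be fixed. The conclusion rests on the text alone: the question is between-arm and about cessation, while the stated outcomes omit abstinence and the stated tests omit any contrast of arms. Under the plan as written, a significant fall in every arm is compatible with no effect of random delivery, and the primary endpoints cannot supply a quit rate. The sizes shown assume 15 analysed per arm, SDs of 30 to 40 percentage points and illustrative means. Other values would change the figures but not the conclusion. The missing comparison is the heavier defect, because it remains even if the objective is reworded as smoking reduction.

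**What to change.** 1. **Define abstinence.** Prespecify CO-verified 7-day point-prevalence abstinence at Visit 5 (Day 42) as the outcome on which any cessation statement rests: no cigarettes in the last 7 days and CO below a stated cut-off. Label window, visit and cut-off as choices; below the 6 ppm entry level is one example. State whether the outcome is primary or secondary, and whether other tobacco use, already asked about at Visit 5, counts against abstinence.
2. **Compare arms.** Analyse all 45 randomized participants by assigned arm. Report the proportion in each arm and the random versus steady-state and random versus placebo differences with exact 95% CIs, presented as estimates.
3. **Settle missing data and diary coding.** At each log review, code a day without a cigarette entry as confirmed zero or unconfirmed. Status is missing if no smoking is recorded but the Visit 5 CO is absent or a day in the window stays unconfirmed. Count missing as smoking by convention, with two sensitivity analyses: observed cases only, and unconfirmed days with film entries counted as zero. Report withdrawals and missing status by arm. Apply the same day rule to CPD.
4. **Keep percent reduction in CPD and CO at Visit 5, described as reduction.** Name the baseline, for example the Day −7 to Day 0 diary for CPD and either the Visit 1 or the Visit 2 value for CO. Compare the same two pairs of arms, for example by baseline-adjusted differences with 95% CIs, and label the paired tests as within-arm description.

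If the sponsor prefers not to add abstinence, restate section 1.1 as smoking reduction and still make change 4.

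**Cost.** Protocol and SAP wording, plus one code entered during a review that is already planned. Diary, other-tobacco and CO data are already collected at Visit 5. The drawbacks are wide intervals for abstinence, and possible bias from counting missing as smoking if withdrawals differ by arm, hence the sensitivity analyses.

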8.0 Subject Numbers and Statistical Plan

8.1 Number of Subjects

Participants will be enrolled in the study until a total of 45 are randomized. We anticipate that we will need to enroll up to 70 participants in order to randomize 45.

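### Two primary endpoints and two comparators have no primary visit, alpha, either/both rule or multiplicity control, and the only stated tests are within-arm changes that cannot decide the hypothesis

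*Combined protocol and SAP*

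**What the plan says.** Section 1.2 names two primary endpoints: "The primary endpoints for the study include the percent reduction in the number of cigarettes smoked", and with it the percent reduction in exhaled CO. It does not say whether success on one is enough or both are needed. Section 1.1 hypothesizes more cessation under random delivery, "as compared to those assigned to a steady state or placebo regimen", which gives two comparators with no order between them.

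The statistical text is short. Section 8.3 reads "Paired sample t-tests (or nonparametric Wilcoxon Rank-Sum tests) will be used to examine changes in the outcome measures" and lists CPD, CO, subjective measures, blood pressure and heart rate. Section 10.7 repeats this for safety: "Paired sample t-test (or nonparametric Wilcoxon Rank-Sum test) will be used to examine the changes in the outcome measures". Neither section names a comparison between arms, an alpha, a sidedness, an analysis visit or an adjustment.

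On size, section 8.1 says "Participants will be enrolled in the study until a total of 45 are randomized", and section 8.2 puts this at 15 per arm. In the Time & Events Table (section 7.1), CO is measured after randomization at Visits 3, 4 and 5 (Days 14, 28 and 42). Cigarette diaries are also collected at the three phone calls. Under section 7.2.4 the quit attempt starts the morning after Visit 3, so only Visits 4 and 5 follow it.

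**The concern.** The hypothesis compares arms, but the planned tests look at each arm against its own baseline. Whoever analyses the trial must therefore add the comparison that answers the question, and nothing in the plan limits how. The endpoint, comparator and visit could all be chosen after the data are seen. A claim for random delivery based on whichever combination came out significant would carry more risk of error than its p-value suggests. With 15 per arm, readers will depend heavily on whether the one result that counts was fixed beforehand.

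**Working it through.** **Inputs.** From the documents: 2 endpoints (1.2), 2 comparators (1.1), 3 arms of 15 (8.1, 8.2), and 3 post-randomization visits with CO, 2 of them post-quit (7.1, 7.2.4). Assumed because the documents are silent: each test at two-sided 0.05, no adjustment, endpoint correlation 0 to 0.9, visit correlation 0 to 0.9. The plan states no error rate, so there is no figure to reproduce.

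**Step 1: what the stated tests can decide.** Suppose the three arms are truly identical and each within-arm test has the same probability p of being significant. The chance that the random arm is significant and at least one other arm is not is p(1 − p²). This is 0.375 at p = 0.5, at most 0.385 (p = 1/√3 = 0.577: 0.577 × 2/3), and 0.171 at p = 0.9. A contrast of within-arm results can therefore look like an advantage up to about 38% of the time, for one endpoint, when there is none. Adjusting for multiplicity would not cure this; a between-arm test is needed.

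**Step 2: between-arm tests without a success rule.** With 2 endpoints × 2 contrasts there are 4 tests per visit. If they were independent:
- one visit: 1 − 0.95^4 = 18.5%
- two visits: 1 − 0.95^8 = 33.7%
- three visits: 1 − 0.95^12 = 46.0%

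They are not independent. The two contrasts share the random arm, so with equal n they correlate at (σ²/n)/(2σ²/n) = 0.5, and endpoints and visits correlate as well. Simulating three identical arms of 15 with two-sample t-tests (28 df, at least 40,000 trials per setting) gives the chance of at least one significant result:

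| Visits used | Tests | Either direction | Favouring random delivery |
|---|---|---|---|
| One | 4 | 13-17% | 6-9% |
| Two post-quit (Visits 4, 5) | 8 | 17-30% | 9-16% |
| Three (Visits 3, 4, 5) | 12 | 20-44% | 10-25% |
| A single test, for reference | 1 | 5% | 2.5% |

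At one visit the either-direction rate is 17.2%, 17.1%, 15.9%, 14.9% and 12.8% for endpoint correlation 0, 0.3, 0.5, 0.7 and 0.9. The two-visit row uses endpoint and visit correlations of 0.3 to 0.9; with both at 0 the rate is 31%. The three-visit row covers 0 to 0.9 for both. Its middle, with endpoint correlation 0.3-0.7 and visit correlation 0.5-0.7, is 31-39% in either direction and 16-20% favouring random delivery.

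**Step 3: if both endpoints must succeed.** Require CPD and CO to be significant for the same contrast at one visit, still unadjusted for two contrasts. The either-direction rate is 0.5%, 0.9%, 1.6%, 3.1% and 5.3% at endpoint correlation 0, 0.3, 0.5, 0.7 and 0.9. Favouring random delivery it is about half that: about 0.5% at correlation 0.3, rising to just under 3% at 0.9.

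**Step 4: does adjustment work?** Testing the four one-visit comparisons at 0.05/4 = 0.0125 brings the either-direction rate to 3.6-4.7%. Holm gives the same figure when no arm differs, because its first step is that same test.

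**The case against.** The strongest reply is that these rates do not describe the plan, because it contains no between-arm tests. That stands: the figures are conditional on adding the tests the hypothesis needs, and on an alpha, sidedness and correlations the documents do not give. The Wilcoxon rank-sum test in section 8.3 is ordinarily a two-sample test, but it is offered there as the alternative to a paired t-test of change from baseline, so it cannot be read as a planned comparison of arms.

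Three further replies also stand in part.
- The hypothesis is directional, so results against random delivery are not the feared error. This halves the rates; at one visit 6-9% is still roughly 2.5 to 3.5 times the 2.5% of a single test.
- Visit 3 precedes the quit attempt, so a cessation claim has two candidate visits. The two-visit row applies.
- Section 1.2 describes the CO reduction as going along with the fall in cigarettes, and section 7.4.4 says CO is there to verify smoking intensity. CO may be meant as corroboration, in which case there is little or no inflation at one visit. The text does not settle this, and the gap between 0.5-3% and 6-9% shows why it should.

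Calling the study exploratory does not answer the point. Section 1.1 aims to determine whether random delivery helps, section 8.2 expresses confidence in the power, and nothing in the supplied text calls it a pilot.

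**Conclusion.** The concern holds as a gap in the decision rule. As written, the plan has no controlled test of its own hypothesis, and supplying between-arm tests without a rule would leave the error rate open: 13-17% at one visit, 17-30% over two post-quit visits and 20-44% over three in either direction, and about half that in favour of random delivery. These ranges rest on unadjusted two-sided 0.05 tests, normal data, full arms of 15 and assumed correlations.

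Two stronger readings are not supported.
- A reader might take a figure such as one in six, or one third, as the trial's actual false positive rate. The documents fix neither the tests nor the alpha, so no single rate can be attributed to the plan.
- A reader might count 2 endpoints × 3 arms × 3 visits = 18 within-arm tests, treat a success on any as support for random delivery, and quote 1 − 0.95^18, about 60%. But everyone enrolled wants to quit and every arm is told to stop smoking after Visit 3, so real falls are expected in all arms and rejecting no change is mostly a true finding. Twelve of the 18 tests are in the other two arms, where a fall is no evidence for random delivery. The count also leaves out the diary data from the phone calls.

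**What to change.** Before unblinding, add a paragraph to section 8.3 that:
1. names Visit 5 (Day 42) as the single primary time point for both endpoints;
2. specifies between-arm tests of random vs placebo and random vs steady state at an overall two-sided 0.05;
3. controls the family by either a fixed testing order or a Holm adjustment, and states whether CO is a separate step or required corroboration of CPD;
4. labels other visits and all within-arm changes as descriptive.

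The order is the sponsor's choice. Starting with CPD is one example. Which comparator goes first needs thought, because placing steady state behind placebo could block the trial's most distinctive question, and the documents do not settle it.

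The change needs no extra participants or procedures. Under a fixed order the first test keeps the full 0.05, but later steps cannot be claimed once one fails. Holm costs power at its first step. For an assumed standardized difference of 1.0 with 15 per arm, the expected z is √(15/2) = 2.74. Approximate power is Φ(2.74 − 1.96) = 78% at 0.05 and Φ(2.74 − 2.50) = 60% at 0.0125, with some of the loss recovered if other comparisons also succeed. Requiring CO to corroborate CPD also lowers power, by an amount that depends on their correlation.

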3.0 Inclusion and Exclusion Criteria

3.1 Inclusion Criteria

1. Aged 18-55
2. Smoke ≥ 10 cigarettes/day for at least the past 12 months
3. Exhaled CO measurement ≥ 6 ppm at baseline visit
4. Interested in completely ceasing cigarette consumption and using a nicotine film product as directed
5. Willing to attend regular visits over a 6-week period (not planning to move, not planning extended vacation, no planned surgeries)
6. Able to read and write in English
7. Able to understand and consent to study procedures

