7.0 Study Design and Procedures

7.1 Study Design

This is a randomized, double-blind, placebo-controlled, parallel-group study that will occur in three phases over 7 weeks.

Time & Events Table								
	Baseline	Pre-Cessation			Cessation			
Study Week Number	-1	0	1	2	3	4	5	6
Study Visit Number	1	2	Ph #1	3	Ph #2	4	Ph #3	5
Study Day Number	-7	0	7	14	21	28	35	42
MEASURES								
Screener 3	X							
Concomitant medications	X	X	X	X	X	X	X	X
Medical history	X							

NIDA Quick Screen	X						
Cigarette details	X						
Adverse events		X	X	X	X	X	X
Daily cigarette/film diary collection		X	X	X	X	X	X
Demographics	X						
Tobacco Use History	X						
Environmental Tobacco Smoke Questionnaire		X		X		X	X
Cigarette Evaluation Scale		X	X	X	X	X	X
Nicotine dependence		X		X		X	X
Minnesota Withdrawal Scale		X		X		X	X
Questionnaire Smoking Urge		X		X		X	X
Perceived Stress		X		X		X	X
Confidence to quit		X		X		X	X
Study product side effects			X	X	X	X	X
Study product evaluation			X	X	X	X	X
Likelihood of Use Scale				X		X	X
Dose Awareness							X
BIOMEASURES							
Height		X					
Weight		X		X		X	X
Waist/Hip ratio		X					X
Exhaled CO	X	X		X		X	X
Blood pressure & pulse	X	X		X		X	X
Pregnancy test	X			X		X	

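### The primary endpoints are percent reductions and the hypothesis compares arms, but the only stated test is a paired within-arm test of change on no named scale

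*Combined protocol and SAP*

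**What the plan says.** Section 1.2 defines the primary endpoints as the "percent reduction in the number of cigarettes smoked and the accompanying percent reduction in exhaled carbon monoxide (CO) levels". It names no visit at which the reduction is assessed and does not say which measurement is the baseline.

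Section 1.1 gives the hypothesis: "smoking cessation will be greater in subjects assigned to a random nicotine delivery regimen (as compared to those assigned to a steady state or placebo". Section 7.1 describes a "randomized, double-blind, placebo-controlled, parallel-group study", and section 8.2 gives 15 participants per arm.

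Section 8.3 is a single sentence: "Paired sample t-tests (or nonparametric Wilcoxon Rank-Sum tests) will be used to examine changes in the outcome measures". It lists CPD and CO alongside subjective ratings, blood pressure and heart rate, with change taken from baseline. Section 10.7 repeats it under safety monitoring: "Paired sample t-test (or nonparametric Wilcoxon Rank-Sum test) will be used to examine the changes in the outcome measures". Neither section mentions a percent, ratio or log scale, a comparison of arms, or adjustment for the baseline value. The only covariate named anywhere is concomitant medication (section 7.4.6.5), and no model is given that could hold it.

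The baseline data needed for a better analysis are already collected. Participants keep a cigarette diary for the week before randomization (7.2.1.10, reviewed under 7.2.2.2), and exhaled CO is measured at Visits 1 and 2 before any film is taken (table in 7.1).

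**The concern.** Two links are broken between what the trial sets out to show and what it will test.

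The first is scale. A paired t-test on CPD or CO is a test of the mean absolute difference, to which heavier smokers can contribute most. Mean percent reduction gives each participant's relative change equal weight. Eligibility sets floors only (at least 10 cigarettes a day, and "Exhaled CO measurement ≥ 6 ppm at baseline visit"), so baselines may vary widely and the two summaries can diverge.

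The second is the contrast. A paired test asks whether an arm changed from its own baseline. Everyone enrolled wants to quit and is told to stop smoking after Visit 3, so a fall is to be expected in every arm, placebo included. Significant falls, or a pattern of significance in one arm and not another, would not answer the question in section 1.1.

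Followed as written, the plan leaves the main conclusion to an informal reading of three separate within-arm results, or to an analysis chosen after the data are seen.

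**Working it through.** **No figure of the plan to reproduce.** 45 randomized / 3 arms = 15 per arm, which agrees with section 8.2. That section gives no effect size, SD, correlation, alpha or power, so nothing further can be checked.

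**1. Absolute versus percent change.** Take three illustrative participants with baselines of 10, 20 and 40 CPD.

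| Reductions | Mean change | Mean percent reduction |
|---|---|---|
| 10, 10, 10 | 30/3 = 10 | (100 + 50 + 25)/3 = 58.3% |
| 0, 0, 30 | 30/3 = 10 | (0 + 0 + 75)/3 = 25.0% |

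The mean change is the same, yet the stated endpoint differs by more than a factor of two.

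**2. What within-arm tests say about arms.** Inputs: n = 15 per arm (section 8.2); two-sided 0.05 and a true within-arm change of 0.5 SD of the differences in both arms (assumptions). The paired t-test then has power 0.438 in each arm (noncentral t, 14 df). The chance that exactly one of two arms is significant is 2 × 0.438 × (1 − 0.438) = 0.49, with no difference between arms. At 0.3 SD it is 0.31 and at 0.7 SD it is 0.41.

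With large changes the failure takes the opposite form. In a simulation of 4,000 trials (baseline CPD of 10 plus a gamma variable with shape 2 and scale 4; individual reductions with SD 0.3, centred on 50% in both arms), the paired test was significant in both arms every time. When one arm was centred on 70% instead, it was again significant in both arms every time. It could not tell equal arms from unequal ones.

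**3. What baseline adjustment could add to a between-arm analysis.** Let r be the correlation of baseline with follow-up and k the baseline SD divided by the follow-up SD. In units of the follow-up variance, the variance of the arm difference is proportional to k² + 1 − 2rk for an unadjusted change score and to 1 − r² for ANCOVA. The ratio is (1 − r²)/(k² + 1 − 2rk), which equals (1 + r)/2 when k = 1. Estimating the slope with three arms and N = 45 multiplies it by about 1 + 1/40 = 1.025.

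| r | k | Ratio | × 1.025 |
|---|---|---|---|
| 0.3 | 1 | 0.65 | 0.67 |
| 0.5 | 1 | 0.75 | 0.77 |
| 0.7 | 1 | 0.85 | 0.87 |
| 0.5 | 0.5 | 0.75/0.75 = 1.00 | 1.03 |
| 0.5 | 2 | 0.75/3 = 0.25 | 0.26 |

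In power terms, at r = 0.5, k = 1 and an assumed arm difference of 0.8 SD (15 per arm, two-sided 0.05, normal approximation), the change score gives Φ(0.8/√(2/15) − 1.96) = Φ(0.23) = 0.59. ANCOVA, with SD √(0.75 × 1.025) = 0.877, gives Φ(2.191/0.877 − 1.96) = Φ(0.54) = 0.71. With k = 1 the variance gain shrinks to about 8% at r = 0.8 and to nothing near r = 0.95.

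The documents give neither r nor k, so these figures are conditional.

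**The case against.** The strongest reply is that section 8.3 never says the change is absolute. Read together with section 1.2, the change it examines could be meant as a percent change. That is fair: absolute change is the natural reading of a paired t-test on CPD or CO, but it is not written. A reader might infer that the plan commits to raw change; the documents support only that it names no scale. The same repair is needed either way, and the reply does not supply the missing contrast.

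It could also be said that the rank-sum test is a two-independent-sample test and so implies a comparison of arms. The sentence offers it as the nonparametric alternative to a paired test of change from baseline and names no arms. It looks like a slip for the signed-rank test, not a planned contrast.

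A reader might further infer that the plan as written throws away the precision shown in step 3 of the working. It does not follow. Those ratios compare two between-arm analyses, and section 8.3 plans neither. A within-arm test has no treatment contrast for a covariate to sharpen. Nor is adjustment free: it costs a slope, and with the follow-up SD twice the baseline SD at r = 0.5 there is no gain. Unequal SDs are plausible here, since entry requires regular smoking and follow-up comes after an instruction to stop.

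Finally, adjustment does not by itself produce a percent reduction. An ANCOVA of untransformed CPD returns a difference in cigarettes per day, so the scale has to be chosen separately. This stands, and it shapes the fix.

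**Conclusion.** The concern holds on two counts that can be read directly from the text: the endpoint is a percent reduction while the stated test names no such scale, and the hypothesis is between arms while the stated test is within arm. The first can more than double or halve the apparent effect in a simple example (58.3% against 25.0% at the same mean change). The second leaves the main hypothesis with no planned test. Under an assumed common change of 0.5 SD, separate paired tests would point to a spurious arm difference about 49% of the time.

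The case for baseline adjustment is sound but its size is not established. With equal SDs, the variance of the arm difference would be about 0.67, 0.77 or 0.87 of that of an unadjusted change score at r = 0.3, 0.5 or 0.7. It could be no better, or much better, under other SD ratios. These figures support the choice of method for the comparison the trial needs; they do not measure a loss in the paired test now planned.

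**What to change.** Rewrite section 8.3, and align 1.2 and 10.7 with it, before unblinding:

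- **Contrast and time.** Make the primary analysis a baseline-adjusted comparison of random delivery with steady state, and of random delivery with placebo, at one named visit such as Visit 5.
- **CO.** Use ANCOVA of log CO on log baseline CO, with the baseline stated (Visit 2, or the mean of Visits 1 and 2). Report the arm effect as a ratio of adjusted geometric means; one minus that ratio is a relative reduction between arms. State a rule for readings of zero. If a constant is added before taking logs, the ratio is only approximately one of CO.
- **CPD.** Compare between arms the percent reduction from the pre-randomization 7-day diary mean to the last-7-day mean, with baseline CPD as covariate and a permutation p-value if many follow-up values are zero. Say how a diary day without an entry is counted, because after the quit date cigarettes are recorded only when there is a slip (7.2.4.9, 7.2.6.8).
- **Paired tests.** Keep them as descriptive within-arm summaries, and name the signed-rank test as the nonparametric version.

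No new visit, measurement or participant is needed. The cost is about one degree of freedom for the slope and a change of wording. Because the statistical plan sits inside the protocol, that means amending the protocol's primary analysis.
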